- 11. Subjects were willing to comply with sun avoidance measures for the face (as well as back/chest and shoulders, if applicable) including use of investigator-approved sunscreen and/or hats, had limited sun exposure time, and had no tanning bed use.
- 12. Subject must have been in good general health as determined by the investigator and supported by the medical history, physical examination, and normal or not clinically significant abnormal vital signs (blood pressure and pulse). Subjects were eligible if:
 - a. Systolic blood pressure (BP) < 160 and > 85 mmHg
 - b. Diastolic BP < 100 and > 50 mmHg
 - c. Pulse 50 to 100 bpm inclusive for adults; up to 110 bpm for subjects < 18 years of age

Exclusion Criteria:

- 1. Females who were pregnant or lactating or planning to become pregnant during the study period.
- 2. Treatment with the following products:
 - a. Topical acne treatments (retinoids, antibiotics, benzoyl peroxide, azelaic acid, resorcinol, salicylates, α-hydroxy/glycolic acid), or other topical facial medication (antifungals, steroids, anti-inflammatories) on the treatment area in the 14 days prior to the Baseline Visit, including prescription and non-prescription products.
 - b. Systemic corticosteroids, systemic acne treatments including systemic antibiotics used for treatment of acne, potential photosensitizing agents (thiazides, phenothiazines), spironolactone, flutamide, or immunosuppressant drugs in the 30 days prior to the Baseline Visit.
 - c. Systemic retinoid use (including high dose vitamin A > 10,000 units per day) in the 180 days prior to the Baseline Visit.
 - d. Undertaken certain facial procedures such as chemical peel, laser treatment, photodynamic therapy, acne surgery, cryodestruction or chemodestruction, x-ray therapy, intralesional steroids, dermabrasion, or depilation (except eyebrow shaping) in the 30 days prior to the

[name], Ltd Statistical Analysis Plan, Version 2.0

Baseline Visit. After the subject is enrolled in the study, eyebrow shaping (except for tweezing) is prohibited.

- e. Treatment with a medication or procedure that, in the opinion of the investigator, would put the subject at unacceptable risk for participation in the study or may interfere with evaluations in the study.
- f. Treatment with an investigational product or device in the 30 days prior to the Baseline Visit.

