4.4. Randomization

Subjects were assigned randomly to one of the four treatment arms, DFD-03 (tazarotene) Lotion 0.1%, Tazorac (tazarotene) Cream, 0.1%, Vehicle Lotion or Vehicle Cream in a 2:2:1:1 ratio (50 subjects each to DFD-03 Lotion and Tazorac Cream, and 25 subjects each to Vehicle Lotion and Vehicle Cream). A treatment assignment schedule was created with kit numbers randomly assigned to study products. The date and time of randomization and the bottle/tube number should have been entered on the eCRF.

[name], Ltd Statistical Analysis Plan, Version 2.0

For the selected site(s) enrolling subjects in the 9-11 age group, subjects were assigned randomly to one of the two treatment arms, DFD-03 (tazarotene) Lotion 0.1%, and 0.1%, Vehicle Lotion in a 1:1 ratio (4 subjects each to DFD-03 Lotion and Vehicle Lotion). A treatment assignment schedule was created with kit numbers randomly assigned to study products, which is independent from the treatment assignment schedule created for ages 12 and older.

For the selected site(s) enrolling subjects with acne involvement on the face, chest and/or back including shoulders, subjects were assigned randomly to treatment with either DFD-03 (tazarotene) Lotion 0.1%, Tazorac (tazarotene) Cream, 0.1%, Vehicle Lotion or Vehicle Cream in a 2:2:1:1 ratio. Since these subjects were treating their face, chest and/or back and shoulders, the subject kit size contained more study medication for application. A treatment assignment schedule was created for these larger kit sizes with kit numbers randomly assigned to study products, which is independent from the treatment assignment schedules created for ages 9-11 and 12 and older.

A unique subject number was assigned to each subject. The randomization number (kit number) was designated as the subject number. The subject maintained the same subject number and treatment assignment throughout the study. Subject numbers were assigned immediately prior to dispensing study medication and were assigned starting with the lowest available number at the study site.

The Investigator designated an independent third party study medication dispenser who dispensed to qualified subjects, collected all bottles/tubes of study product and dispensed and collected diaries.

No stratification based on age or other characteristics was performed.

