9.6. Vital Signs

The following vital sign parameters will be summarized by visit and treatment group:

- Diastolic Blood Pressure (mm Hg)
- Systolic Blood Pressure (mm Hg)
- Pulse Rate (beats/min)

In general, if multiple results are reported within the given analysis visit window for the same parameter, the mean of the results will be used for summary statistics except for baseline, for which the last assessment will be used.

For all vital sign parameter, the continuous results will be summarized using descriptive statistics by visit and treatment group. The summary statistics are n, mean, median, SD, minimum and maximum. Boxplots for vital signs versus time by treatment for all time points will also be generated. Boxplots will display Baseline, Day 28, Day 56 and Day 84 assessments.

Changes from baseline will also be summarized by visit and treatment. The summary statistics are n, mean, median, SD, minimum and maximum. With respect to the mean change from baseline, the 95% confidence interval will also be computed. Boxplots for change from baseline versus time by treatment for all time points will also be generated. Boxplots will display Day 28, Day 56 and Day 84 assessments.

Potentially Clinically Significant (PCS) vital signs will be summarized by parameter. The summary will indicate the number of subjects with PCS-low or PCS-high values by visit and treatment group. The criteria for identifying PCS abnormalities for vital signs are summarized in Table 15.8,9

Table 15: Criteria for Potentially Clinical Significant Vital Sign Abnormalities

		Criteria	
Parameter	Age	PCS Low	PCS High
Pulse	5 to 14 years	\leq 50 bpm at any time post dose.	\geq 140 bpm at any time post dose.
(beats/min)	15 to 18 years	\leq 50 bpm at any time post dose.	\geq 120 bpm at any time post dose.
	18 and above	\leq 50 bpm at any time post dose.	\geq 110 bpm at any time post dose.
	Any	Any \geq 15 bpm decrease from baseline at any time post dose.	Any \geq 15 bpm increase from baseline at any time post dose.
Systolic Blood	7 to 12 years	≤ 117 mm HG at any time post dose.	≥ 130 mm Hg at any time post dose.
Pressure (mm Hg)	13 to 17 years	≤ 120 mm HG at any time post dose.	≥ 144 mm Hg at any time post dose.
	18 and above	≤ 90 mm HG at any time post dose.	≥ 150 mm Hg at any time post dose.
	Any	Any \geq 20 mm Hg decrease from baseline at any time post dose.	Any \geq 20 mm Hg increase from baseline at any time post dose.

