Diastolic Blood	7 to 12 years	≤ 75 mm HG at any time post dose.	≥ 86 mm Hg at any time post dose.
Pressure (mm Hg)	13 to 17 years	≤ 80 mm HG at any time post dose.	≥ 92 mm Hg at any time post dose.

		Criteria	
Parameter	Age	PCS Low	PCS High
	18 and above	≤ 50 mm HG at any time post dose.	≥ 100 mm Hg at any time post dose.
	Any	Any \geq 15 mm Hg decrease from baseline at any time post dose.	Any \geq 15 mm Hg increase from baseline at any time post dose.

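### SAP Table 15 lets a change from baseline alone count as potentially clinically significant, so the counts mix limit breaches with visit-to-visit variation; the pulse age bands overlap, and the under-18 low limits catch ordinary readings

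*SAP*

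**What the plan says.** SAP Section 9.6 plans a PCS summary by parameter: "The summary will indicate the number of subjects with PCS-low or PCS-high values by visit and treatment group". Table 15 supplies the criteria. Each of pulse, systolic and diastolic pressure has absolute low and high limits by age band, then a row for any age with a change condition only. The low conditions are at least a "15 bpm decrease from baseline at any time post dose" for pulse, a "20 mm Hg decrease from baseline at any time post dose" for systolic pressure and a "15 mm Hg decrease from baseline at any time post dose" for diastolic pressure. The high column has increases of the same sizes.

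The SAP does not say whether the rows combine by OR or by AND. Neither the index of tables nor the vital-sign table shell contains a PCS display that would settle it.

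The pulse bands are 5 to 14, 15 to 18, and 18 and above. The blood pressure bands are 7 to 12, 13 to 17, and 18 and above. For ages 13 to 17 the low limits are 120 mm Hg systolic and 80 mm Hg diastolic; for ages 7 to 12 they are 117 and 75.

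**The concern.** Because the change condition has its own row, the plain reading is that either row is enough. An adult pulse going from 85 to 70 bpm is then PCS low, and an adult systolic pressure going from 110 to 130 mm Hg is PCS high. All four readings lie inside the adult limits (50 and 110 bpm; 90 and 150 mm Hg). Counts built this way pool two different things: readings outside a limit, and differences that may be ordinary variation between visits. A programmer who took the rows to combine by AND would produce very different counts from the same data.

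Two further faults in the table change the counts. An 18-year-old with a pulse of 110 to 119 bpm is PCS high under one band and not under the other. And the under-18 low limits sit so high that ordinary adolescent blood pressures meet them.

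Vital signs are a secondary safety endpoint and the PCS summary is descriptive, so what is at stake is how readable one safety table is.

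**Working it through.** **No plan figure to reproduce.** The documents state no expected PCS rate and no vital-sign SD.

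**Inputs from the documents**
- Change thresholds t: 15 bpm, 20 mm Hg systolic, 15 mm Hg diastolic (SAP Table 15).
- Three post-baseline assessments: "Boxplots will display Day 28, Day 56 and Day 84 assessments" (SAP 9.6).
- Repeat results in a window are averaged "except for baseline, for which the last assessment will be used" (SAP 9.6), so the error in one baseline reading enters every change.
- Arms: "50 subjects each to DFD-03 Lotion and Tazorac Cream, and 25 subjects each to Vehicle Lotion and Vehicle Cream" (SAP 4.4).

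**Assumption.** Within-subject visit-to-visit SD s of 5-10 bpm for pulse, 6-10 mm Hg for systolic and 5-8 mm Hg for diastolic pressure; normal errors; no drug effect.

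**One cell (one parameter, one visit, one direction).** The change has SD s√2, so P = 1 − Φ(t / (s√2)).
- t = 15, s = 5: 15/7.07 = 2.12, P = 1.7%
- t = 15, s = 8: 15/11.31 = 1.33, P = 9.2%
- t = 15, s = 10: 15/14.14 = 1.06, P = 14.4%
- t = 20, s = 6: 20/8.49 = 2.36, P = 0.9%
- t = 20, s = 10: 20/14.14 = 1.41, P = 7.9%

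The planned cells therefore run at about 1-15%. That is 0.5 to 7.5 subjects in an arm of 50 (50 × 0.01, 50 × 0.15) and 0.25 to 3.75 in an arm of 25.

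**Any parameter, any of three visits.** The three changes share a baseline, so the per-parameter rate was simulated (400,000 subjects). Parameters were combined as independent: 1 − (1 − a)(1 − b)(1 − c). At SDs 5/6/5 (pulse/systolic/diastolic), 1 − 0.912 × 0.951 × 0.912 = 21%. At 10/10/8, 1 − 0.418 × 0.647 × 0.594 = 84%.

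| SDs | Unrounded | Rounded to integers |
|---|---|---|
| 5/6/5 | 21% | 24% |
| 6/6/5 | 30% | 33% |
| 8/8/6 | 61% | 64% |
| 10/10/8 | 84% | 86% |

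The SAP's vital-signs listing shows pulse and blood pressure as whole numbers, so rounding is the closer model. A systolic-diastolic correlation of 0.6 lowers the unrounded figures by 1-3 points. Nearly all these flags fall on readings inside the adult limits: 20.3 of 20.9 points at 5/6/5 and 80.8 of 83.9 at 10/10/8. This split also assumes means of 75 bpm and 118/72 mm Hg with between-subject SDs of 8, 10 and 7.

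**Age 18.** The pulse band 15 to 18 has a high limit of 120 bpm; the band 18 and above has 110. Both contain age 18. The blood pressure bands split at 17/18 and do not overlap.

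**Under-18 low limits.** Eligibility requires systolic pressure above 85 and below 160, and diastolic above 50 and below 100. At ages 13 to 17 the low limits make systolic 86-120 and diastolic 51-80 PCS low. Only 121-143 and 81-91 escape both absolute limits, the high limits being 144 and 92. A 15-year-old at 110/70 is eligible, unchanged, and PCS low on both. If adolescent systolic pressure has mean 105-115 and SD 10-12, 68-94% of readings are at or below 120. If diastolic has mean 65-75 and SD 8-10, 71-97% are at or below 80.

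**The case against.** The label says only potentially significant, and a deliberately sensitive screen is defensible. Table 15 cites outside criteria, not available here, which may say how the rows combine. Noise falls on all randomised arms alike. Section 9.6 also plans mean changes with 95% confidence intervals, and Protocol Section 8.2 makes a post-baseline vital sign an adverse event on the investigator's judgment, not on the PCS flag. All of this stands, and it limits the consequence. It does not remove the ambiguity, because the SAP itself has to say how the rows combine.

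Three stronger readings are tempting, and the documents do not support them.

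- *A third or more of subjects would be flagged.* This needs an SD that the documents do not give, and it counts any parameter at any visit, which the SAP does not plan to report. At SDs 5/6/5 the figure is 21-24%. For one parameter at one visit, both directions together, one third needs an SD of at least 11.0 (15-unit rows) or 14.6 (20-unit row). The protocol fixes neither position nor number of readings, so the SD cannot be inferred.
- *Vital signs could then neither show nor rule out a signal.* The mean-change analyses and the adverse-event tables remain.
- *PCS should require both a limit breach and a change.* That is a trade-off in sensitivity. In adults it cuts the any-flag share sharply (21% to 0.7% at 5/6/5; 84% to 12% at 10/10/8) but drops large in-range changes. At ages 13 to 17 it would barely touch low flags. To fall by 15 mm Hg and stay above 80, diastolic pressure must start at 96 or more (81 + 15), against an eligibility ceiling below 100. For systolic, the start must be 141 or more (121 + 20).

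**Conclusion.** The point holds as a fault in how Table 15 is specified. On its plain wording, a change between two readings inside the adult limits is PCS, and the PCS counts would mix limit breaches with visit-to-visit variation. The size depends on the assumed within-subject SD. For SDs of about 5 to 10, roughly 20-85% of subjects would have at least one change-only flag over the study, and about 1-15% would in each cell the SAP plans to show.

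The age-18 overlap is a definite inconsistency and needs no assumption. It affects only 18-year-olds with a pulse of 110 to 119 bpm. The under-18 low limits are the larger fault. That eligible, unchanged readings meet them follows from the documents alone; that most ordinary readings would do so rests on the assumed adolescent means and SDs. The trial enrols from age 12, plus about eight subjects aged 9 to 11, so this is not a marginal group by design.

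The effect is confined to one descriptive summary of a secondary safety endpoint.

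**What to change.** Before database lock, amend SAP Section 9.6 and Table 15 as follows.

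1. State how the limit rows and the change rows combine.
2. Report three separate rows per parameter, direction, visit and arm: limit breach only, change only, and both. Change-only counts are then not pooled with limit breaches.
3. Make the pulse age bands mutually exclusive, in line with the 13-17 / 18-and-above split already used for blood pressure.
4. Have the sponsor reconcile the under-18 PCS-low limits with the cited source and with the eligibility ranges. This review does not propose replacement values.
5. Add a PCS table shell, so that the logic is fixed before unblinding.

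The cost is a text edit, one shell and a few more table rows, with no new data and no burden on subjects. The limit-breach rows will hold fewer values than a pooled PCS count would, but every reading stays in the listing and in the change summaries.

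### SAP Table 15 sets the under-18 low blood-pressure limits 25–30 mmHg above the adult limits, so an unchanged 112/70 is flagged low at 17 but not at 18

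*SAP*

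**What the plan says.** SAP 9.6 plans a summary of PCS vital signs that counts flagged subjects, low or high, per visit and arm. Table 15 defines the flags.

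- **Systolic, absolute PCS Low:** "≤ 117 mm HG at any time post dose" at 7–12 years, "≤ 120 mm HG at any time post dose" at 13–17, and "≤ 90 mm HG at any time post dose" at 18 and above.
- **Diastolic, absolute PCS Low:** "≤ 75 mm HG at any time post dose", "≤ 80 mm HG at any time post dose" and "≤ 50 mm HG at any time post dose" for the same three bands.
- **Absolute PCS High:** this rises with age. Systolic is 130, then "≥ 144 mm Hg at any time post dose", then 150; diastolic is 86, then "≥ 92 mm Hg at any time post dose", then 100.
- **Change rows (any age):** a move from baseline of at least 20 mmHg systolic or 15 mmHg diastolic is PCS Low if a fall and PCS High if a rise.
- **Pulse:** the absolute PCS Low limit is 50 bpm in every band. PCS High is 120 bpm in the band for 15 to 18 years and 110 bpm in the band for 18 and above.

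The SAP text gives no reason for the under-18 blood-pressure limits. It cites references 8 and 9 for the table and does not reproduce them. Inclusion Criterion 12 uses one blood-pressure range for all ages: systolic above 85 and below 160, diastolic above 50 and below 100. Enrolment starts at 12 years, with about 8 further subjects aged 9–11.

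**The concern.** Only the under-18 blood-pressure low cells break the table's pattern. The high limits climb in order with age and the pulse low limit is constant, but the blood-pressure low limits rise slightly from 7–12 to 13–17 and then drop by 30 mmHg on both measures at 18. The step appears in both under-18 bands and both measures, so a single damaged cell is an unlikely explanation.

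A low flag should mark an unusually low reading. Here an adolescent can enter the trial already at or below the limit and be counted without any change. An adolescent can also be counted low at a visit where the pressure has risen enough to be flagged high.

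Age mix is also not the same in every arm. The 9–11-year-olds are randomised only to DFD-03 Lotion or Vehicle Lotion, planned at 4 each (SAP 4.4), so any excess flags in that group fall only on the lotion side. That concerns about 4 subjects per lotion arm; it is a head count, not a forecast. If PCS counts are carried into the safety subgroups of SAP 8.2, the 17–64 group would mix two rules, because its 17-year-olds fall under the under-18 cells.

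**Working it through.** All inputs are the Table 15 cells and the Criterion 12 limits (whole-number entry range: systolic 86–159, diastolic 51–99). No distribution is assumed. The plan gives no figure of its own to reproduce.

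**1. Gap to the adult row** (under-18 PCS Low minus adult PCS Low)

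- Systolic: 117 − 90 = 27; 120 − 90 = 30 mmHg.
- Diastolic: 75 − 50 = 25; 80 − 50 = 30 mmHg.

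**2. Unchanged 112/70**

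- Age 17: 112 ≤ 120 and 70 ≤ 80, so PCS Low on both measures.
- Age 18: 112 > 90 and 70 > 50, so PCS Low on neither.
- With zero change no change row applies, and no absolute PCS High limit is reached at either age. The blood-pressure bands 13–17 and 18 and above do not overlap, so the contrast is unambiguous.

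**3. Values flagged neither low nor high by the absolute cells**

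| Age | Systolic | Diastolic |
|---|---|---|
| 7–12 | 118–129 (12 values) | 76–85 (10) |
| 13–17 | 121–143 (23) | 81–91 (11) |
| 18 and above | 91–149 (59) | 51–99 (49) |

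**4. Entry values already at or below the PCS Low limit**

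| Age | Systolic (of 74 allowed) | Diastolic (of 49 allowed) |
|---|---|---|
| 7–12 | 86–117 (32) | 51–75 (25) |
| 13–17 | 86–120 (35) | 51–80 (30) |
| 18 and above | 86–90 (5) | none |

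**5. Low and high at the same visit**

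A reading is absolute PCS Low and PCS High by change when it is at or below the low limit after a rise of at least 20 (systolic) or 15 (diastolic). The baseline must then be at most the low limit minus that rise.

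- Systolic: 117 − 20 = 97; 120 − 20 = 100; 90 − 20 = 70. Eligible baselines are 86–97 at 7–12, 86–100 at 13–17, and none in adults.
- Diastolic: 75 − 15 = 60; 80 − 15 = 65; 50 − 15 = 35. Eligible baselines are 51–60, 51–65, and none in adults.
- Example: 100/65 to 120/80 is a rise of 20 and 15. At 17 it is PCS Low (120 ≤ 120, 80 ≤ 80) and PCS High by change on both measures. An adult with the same readings is PCS High only.
- The opposite conflict (absolute PCS High after a qualifying fall) is possible only for systolic pressure at 7–12, from baselines 150–159 (130 + 20 = 150).

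**6. Pulse bands**

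Age 18 belongs to two bands with different high limits (120 and 110 bpm), so a pulse of 110–119 at 18 is PCS High under one row only. The absolute low limit is 50 in both, so PCS Low is unaffected.

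Steps 3 to 5 describe the rule, not expected proportions of subjects.

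**The case against.** **The affected display may never be produced.** The SAP's display index has one vital-signs summary, covering results and change from baseline, and its shell has no PCS rows. Protocol 11.5.5 asks only for changes from baseline. This stands as a limit on consequence. The text of SAP 9.6 still commits to the PCS counts, so the rule should be right before anyone programs it.

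**Table 15 does not say whether the absolute and change rows apply separately or jointly.** Under a joint rule an unchanged reading is never flagged and the double flag cannot occur. The change criteria have their own row, so separate application is the natural reading, but steps 2, 4 and 5 do depend on it. The break at 18 does not: a fall from 132 to 112 (20 mmHg) would be PCS Low under a joint rule at 17 (112 ≤ 120) and not at 18 (112 > 90).

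**Entry limits overlap PCS limits in adults too.** Adults may enter at systolic 86–90 (PCS Low), systolic 150–159 (PCS High) or pulse 50 (PCS Low). So overlap alone proves nothing. Its size differs greatly, however: 35 of 74 systolic values at 13–17 against 5 of 74 in adults. It also does not explain a low limit that can be met after a qualifying rise.

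**The intended values are unknown.** This is correct. Inflated here means relative to the adult row; the documents cannot show which cells are wrong or why.

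**No comparison across age 18 is planned, and no between-arm bias is shown.** From age 12 upward, randomisation covers all four arms, and the SAP 8.2 age groups do not split at 18. The vital-signs listing also shows every reading with a clinical-significance field. These points keep the matter small; they do not make the counts interpretable.

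**Conclusion.** The point holds. The four under-18 PCS Low blood-pressure cells lie 25 to 30 mmHg above the adult cells without explanation. Applied as printed, with the rows read as separate criteria, they would give under-18 PCS-low counts that are inflated relative to the adult rule and not comparable across age 18.

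The consequence is minor. It reaches one descriptive summary of a secondary safety endpoint. The primary endpoints, the continuous vital-sign summaries and adverse events judged by the investigator do not use Table 15. The change-from-baseline criteria do not use these cells and stay informative if shown on their own. The share of subjects flagged cannot be stated: the documents give no blood-pressure distribution and no count of under-18s beyond the 8 or so aged 9–11. The pulse overlap at 18 is a smaller defect in the same table.

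**What to change.** Before programming:

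1. Check the four under-18 PCS Low blood-pressure cells against references 8 and 9 and reconcile them with the adult row. If they are not lower limits, correct them. If they are intended as printed, add a written justification for the break at 18. No value is proposed here.
2. State that the absolute and change-from-baseline criteria are separate, and tabulate them separately.
3. Make the pulse age bands mutually exclusive. A break at 18 matches the blood-pressure rows and the age split for pulse in Criterion 12.

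The cost is a source check, four table cells to correct or justify, one age label and one sentence in the SAP. No protocol change and no new data are needed.
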